Name: (please print): [name] Position: Professor of Biostatistics Date: 10/MAY/2017

KEY TRIAL CONTACTS

Chief Investigator	[name], Department of Clinical Sciences, Liverpool School of Tropical Medicine; Honorary Consultant Paediatrician, Alder Hey NHS Foundation Trust. [contact]; [contact]
Study Co-ordinator	Alder Hey Research Nurse: to be appointed
Sponsor	Alder Hey Children's NHS Foundation Trust, [name]. [contact]; e mail: [contact]
Joint-sponsor(s)/co-sponsor(s)	Liverpool School of Tropical Medicine, [name]; [contact]; e mail: [contact]
Funder(s)	NIHR Research for Patient Benefit
Clinical Trials Unit	Tropical Clinical Trials Unit, Liverpool School of Tropical Medicine, [name]; e mail: [contact]
Key Protocol Contributors	Full contact details including phone, email and fax numbers (If applicable)
Statistician	[name], Professor of Biostatistics, Liverpool School of Tropical Medicine, [name]; e mail: [contact]
Trials pharmacist	N/a
Committees	TMG: [contact]; [contact]

TRIAL SUMMARY

Trial Title	Evaluation of faecal volatile organic compounds in the diagnosis of paediatric inflammatory bowel disease		
Internal ref. no. (or short title)	Faecal volatiles in children with inflammatory bowel disease		
Clinical Phase	N/a		
Trial Design	Observation study of diagnostic test		
Trial Participants	Children (age <18 years) attending clinics in 3 paediatric gastroenterology referral centres in the UK in whom clinical assessment indicates that IBD is a possibility		
Planned Sample Size	286 children		
Treatment duration	N/a		
Follow up duration	3 months for each child recruited		
Planned Trial Period	April 1st 2017 to September 30 th 2019		
	Objectives	Outcome Measures	
Primary	To evaluate whether faecal VOCs at initial presentation to specialist paediatric gastroenterology services can distinguish children with IBD from those with other common gastrointestinal disorders	Faecal VOCs in IBD versus non-IBD gastrointestinal conditions at initial presentation to specialist paediatric gastroenterology review	
Secondary	To evaluate whether faecal VOCs at initial presentation in children with IBD can distinguish between disease type (Crohn's disease, ulcerative colitis, indeterminate colitis), distribution and severity To evaluate whether the	Faecal VOCs in children according to IBD diagnosis, distribution and severity at initial presentation Faecal VOCs in IBD according	
	faecal VOCs in children with IBD after 3 months of treatment can distinguish those in clinical remission from those with persistent disease	to disease course at 3 months after diagnosis	

	To explore whether the	Analysis of likely source of
	faecal VOCs identified in	the faecal VOCs that differ
	paediatric IBD provide new	between IBD and other GI
	insights into underlying	diseases and correlation with
	disease mechanisms	possible disease mechanisms
Investigational Medicinal Product(s)	N/a	
Formulation, Dose, Route of	N/a	
Administration		

FUNDING AND SUPPORT IN KIND

FUNDER(S) (Names and contact details of ALL organisations providing funding and/or support in kind for this trial)	FINANCIAL AND NON FINANCIALSUPPORT GIVEN
NIHR Research for Patient Benefit; Central Commissioning Facility	Funding awarded: £239,680
[name] [contact]	

ROLE OF STUDY SPONSOR AND FUNDER

The sponsor will be responsible for facilitating staff recruitment at Alder Hey, initiating and supporting the study, holding and disbursing the research funds, confirmation that ethical approval has been secured, prompt reporting of any suspected unexpected serious adverse events or reactions and ensuring that the study is conducted to an appropriate level of scientific quality.

The funder has assessed the scientific quality of the proposed research, confirmed its value for money and considered the suitability of the research environment and experience/expertise of the researchers. The funder will not have any role in the conduct of the study, the data analysis and interpretation, manuscript writing, and dissemination of results.

Neither the sponsor nor the funder will control the final decision regarding any of these aspects of the study.

ROLES AND RESPONSIBILITIES OF TRIAL MANAGEMENT COMMITEES/GROUPS & INDIVIDUALS

Trial Management Group

We will establish a Trial Management Group (TMG) comprised of the CI, lead clinicians (PIs) at each centre, the statistician, Laboratory Supervisor, Data Manager, Alder Hey Research Nurse, and two PPI members. The TMG will be independent of the sponsor. The TSC will hold monthly teleconferences to advise and oversee the overall conduct and progress of the study including recruitment to target, data management and data analysis. We will appoint an external senior paediatric gastroenterologist experienced in research (volunteer) to join the TMG meetings every 6 months to ensure that the study progresses according to GCP principles.

Data Monitoring and Trial Steering Committees are not required for this study given the minimal risk to participants and with no interim analysis planned.

KEY WORDS:

Children; faecal volatile organic compounds; inflammatory bowel disease; diagnosis; pathogenesis

LIST of CONTENTS

GENERAL INFORMATION	Page No.
TITLE PAGE	2
RESEARCH REFERENCE NUMBERS	2
SIGNATURE PAGE	3
KEY TRIAL CONTACTS	4
TRIAL SUMMARY	5
FUNDING	6
ROLE OF SPONSOR AND FUNDER	6
ROLES & RESPONSIBILITIES OF TRIAL MANAGEMENT COMMITTEES, GROUPS AND INDIVIDUALS	7
LIST of CONTENTS	8
LIST OF ABBREVIATIONS	9
TRIAL FLOW CHART	10
SECTION	
1. BACKGROUND	12
2. RATIONALE	14
3. OBJECTIVES AND OUTCOME MEASURES/ENDPOINTS	14
4. TRIAL DESIGN	16
5. STUDY SETTING	16
6. ELIGIBILITY CRITERIA	16
7. TRIAL PROCEDURES	17
8. TRIAL MEDICATION	21
9. PHARMACOVIGILANCE	22
10. STATISTICS AND DATA ANALYSIS	22
11. DATA HANDLING	24
12. MONITORING, AUDIT & INSPECTION	25
13. ETHICAL AND TRIAL ADMINISTRATION	25
14. DISSEMINATION POLICY	28
15. REFERENCES	29
16. APPENDICIES	31

LIST OF ABBREVIATIONS

CI	Chief Investigator	
CRF	Case Report Form	
DMC	Data Monitoring Committee	
GCP	Good Clinical Practice	
IBD	Inflammatory bowel disease	
ICF	Informed Consent Form	
ICH	International Conference on Harmonisation of technical requirements for registration of pharmaceuticals for hum use.	
IDMC	Independent Data Monitoring Committee	
ISF	Investigator Site File	
ISRCTN	International Standard Randomised Controlled Trials Number	
LSTM	Liverpool School of Tropical Medicine	
N/a	Not applicable	
NHS R&D	National Health Service Research & Development	
PI	Principal Investigator	
PIS	Participant Information Sheet	
QA	Quality Assurance	
REC	Research Ethics Committee	
SOP	Standard Operating Procedure	
TMG	Trial Management Group	
TSC	Trial Steering Committee	
TMF	Trial Master File	
VOCs	Volatile organic compounds	

STUDY FLOW CHART

VOCs in pIBD Flow chart

Study timeline

A. Study preparation: April - September 2017 (6 months)

- Study preparation will start on April 1st
- Ethical approval secured by end of July 2017
- SOPs and CRFs completed by end of August 2017
- Study database completed by end of September 2017
- Site-set-up and training completed by end of September 2017

B. Recruitment and follow-up: October 2017 - end of March 2018

- Recruitment across 3 sites (3-4 IBD cases and 3-4 non-IBD controls/centre/month).
- Follow-up of last cases for 3 months (Jan 2019 March 2019)

C. Analyses

- Measurement of faecal VOCs completed by end of March 2019
- Statistical analysis to determine VOCs profiles completed by end of April 2019
- Statistical analysis combining VOCs profile with demographic, clinical and environmental data completed by end of June 2019

D. Writing-up and presentation of findings

• Final report submitted by end of September 2019

STUDY PROTOCOL

Evaluation of faecal volatile organic compounds in the diagnosis of paediatric inflammatory bowel disease

1 BACKGROUND

Inflammatory bowel disease (IBD) is a growing and significant problem in childhood. The diagnosis and monitoring of IBD in children is highly invasive and is accompanied by risk, stress/anxiety for children and families and significant use of healthcare resources. Children, young people and families have told us that a non-invasive diagnostic test is a priority for the NHS.

IBD is an incurable chronic, relapsing condition of unknown aetiology (Day 2012). Its frequency has increased markedly across the world in recent years with the highest prevalence reported in Europe (322/100,000 population for CD; 505/100,000 for UC; Molodecky 2012). A marked increased incidence has been seen in children especially in the Northern Hemisphere and largely due to an increase in Crohn's disease (Malmborg 2016). Up to 25% of IBD starts in childhood or adolescence (Benchimol 2011).

Early-onset IBD, possibly due to inheritance of a greater number of susceptibility genes and/or earlier exposure to environmental triggers, differs from that occurring in adults. In children, inflammation occurs most commonly in the colon complicating differentiation between CD and UC. Early-onset CD is more common in boys (whereas adult-onset disease occurs more commonly in females) and tends to be more extensive with greater involvement of the upper intestine. Colonic inflammation in children with UC also tends to be more extensive than in adults (Benchimol 2011; Day 2012).

At initial presentation in all suspected children, upper and lower intestinal endoscopy (requiring two days of bowel cleansing and usually a general anaesthetic) and small bowel imaging by magnetic resonance enterography or wireless capsule endoscopy are required (Levine 2014). Although serious adverse events are uncommon, these invasive investigations are highly stressful for children and their families and consume considerable hospital resources. Undertaking these investigations delays diagnosis and the start of treatment.

Accurate, non-invasive, rapid and cost-effective diagnostic tools that can be used in the clinic or ward setting and better means of differentiating CD from UC are needed. Faecal calprotectin (FC), a non-specific marker of intestinal inflammation, is recommended by NICE to distinguish IBD from non-inflammatory gut disorders such as irritable bowel syndrome

(http://www.nice.org.uk/guidance/dg11) and a near-patient test has been developed (http://www.buhlmannlabs.ch/core/quantum-blue/calprotectin/). A recent meta-analysis (394 IBD/321 non-IBD controls) reported a pooled sensitivity and specificity of FC in the diagnosis of IBD in children of 0.98 (95% confidence interval: 0.95–1.0) and 0.68 (0.50– 0.86) respectively (Henderson 2014). The low specificity indicates that an alternative or additional test with higher specificity is needed to reduce the time to diagnosis and avoid many children undergoing unnecessary investigations.

There is great interest in the measurement of volatile organic compounds (VOCs) in breath and vapours from various human tissues (urine, stool, blood) in the diagnosis and monitoring of a wide range of diseases. VOCs emitted from stool are responsible for stool odour and consist of a large number of carbon based molecules of low molecular mass (<1.5Kd) including organic acids, alcohols, esters, heterocyclic compounds, aldehydes, ketones and alkanes. They result from the metabolism of the intestinal mucosa and the gut microbiota and their abundance changes according to the specific effects of intestinal diseases on these processes (Chan 2016).

We have demonstrated that faecal VOCs are relatively stable over time within and between individuals despite day-to-day variation in diet and are not affected by freezing and storage of stool samples ([name]; personal communication; PhD Thesis). We have optimized procedures for stool handling for metabolite extraction for gas chromatography-mass spectrometry (GC-MS) analysis (sample volume, solid phase micro-extraction fibre coating, extraction conditions [temperature and time] and vial volume; Reade 2014) and also developed the advanced statistical methods required for determining and comparing VOC profiles (Aggio 2016).

We have shown that the analysis of VOCs separates adult patients with diarrhoea-predominant irritable bowel syndrome (n=30) from those with active CD (62) and UC (n=48; sensitivity of 94% and 96% and specificity of 82% and 80% respectively; p<0.05). Our data in adults strongly suggests that VOCs differentiate CD from UC, and also Crohn's colitis from UC (Ahmed 2013). More recently, we have shown that VOCs also distinguish between active and inactive CD and UC in adult patients (Ahmed 2016).

Despite these encouraging findings, given the differences in IBD between adults and children and that gut microbiota changes with age (O'Toole 2015), we can not assume that diagnostic tests that are effective in adults will necessarily work in children. Therefore, this technology needs to be tested in children. In a proof of principle study, faecal VOCs differentiated children with IBD from healthy children both during active disease and remission (de Meij 2014). However, we are not aware of any previous studies in children that have evaluated the utility of faecal VOCs in differentiating IBD from other common gastrointestinal disorders in an out-patient setting or in monitoring response to treatment.

In light of the changes in the gut microbiota (O'Toole 2015), we would like to assess the fungal microbiome (the mycobiome) the faeces at the time same of samplings a some of the VOCs we have found in association with IBD, in adults, appear to be fungal metabolites (Ahmed 2016). We will investigation the relationship between VOCs and fungi in the children we study.

Measurement of VOCs in fresh stool samples using bench-top equipment in the clinic or ward will be possible in the near future. The University of Liverpool owns the intellectual property for the development of a point-of-care instrument. The development of this technology is supported by the University of Liverpool and Cancer Research UK (the latter for measurement of VOCs in urine to detect bladder and prostate cancer). Industrial partners are engaged in refining the prototype ready for moulding and production this year. The aim is to have a fully tested, CE marked, point-of-care

Faecal volatiles in children with inflammatory bowel disease

instrument on sale in the EU for bladder and prostate cancer in 2020/1 and for IBD/irritable bowel syndrome in 2022.

2 RATIONALE

Our hypotheses are that:

- 1. the measurement of faecal VOCs can distinguish children presenting with IBD from those presenting with other common gastrointestinal disorders
- 2. the measurement of faecal VOCs in children treated for IBD can distinguish those in clinical remission from those with persistent disease
- 3. the faecal mycobiome will be altered during relapse

Measurement of faecal VOCs may replace current more invasive, stressful and expensive investigations/procedures used to diagnose and monitor the progression of IBD such as blood and stool tests, gastrointestinal endoscopy and small bowel imaging by magnetic resonance enterography or wireless capsule endoscopy. Measurement of faecal VOCs may also provide a more rapid initial diagnosis than current investigations/procedures thereby allowing specific treatment to start earlier.

Investigation the temporal relationship between fungi, VOCs and disease activity may enable us to speculate on the role of fungi in relapse and the potential for VOCs to be used a biomarkers.

We are not aware of any current research that is evaluating the potential of VOCs to diagnose IBD in children. ClinicalTrials.gov holds details of a study to validate VOCs in breath and blood in adults with established Crohn's disease (NCT02641171) and of a biobank study that includes analysis of VOCs in breath for diagnosis and response to treatment in adults with IBD (NCT02130349). There are no studies registered with the ISRCTN or European Union Clinical Trials Registers. We are not aware of any commissioned calls on this or related topics through the NIHR Health Technology Assessment or other programmes.

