3 OBJECTIVES AND OUTCOME MEASURES/ENDPOINTS

Our main research questions are:

1. Does the measurement of faecal VOCs distinguish children presenting with IBD from those presenting with other common gastrointestinal disorders?

2. Does the measurement of faecal VOCs in children treated for IBD distinguish those in clinical remission from those with persistent disease?

3. How does the faecal mycobiome change during relapse and what is the relationship to the VOCs?

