3.2 Secondary objectives

- To evaluate whether faecal VOCs at initial presentation in children with IBD can distinguish between disease type (Crohn's diseases, ulcerative colitis, indeterminate colitis), distribution and severity
- To evaluate whether faecal VOCs in children with IBD after 3 months of treatment can distinguish those in clinical remission from those with persistent disease
- To explore whether the faecal VOCs identified in paediatric IBD provide new insights into underlying disease mechanisms
- To explore the relationship between fungi, relapse and VOCs.

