3.3 Outcome measures/endpoints

Primary: Faecal VOCs in IBD versus non-IBD gastrointestinal conditions at initial presentation to specialist paediatric gastroenterology review

Secondary:

- Faecal VOCs in children according to IBD diagnosis, distribution and severity at initial presentation
- Faecal VOCs in IBD according to response to treatment at 3 months after diagnosis
- Analysis of likely source of the faecal VOCs that differ between IBD and other GI diseases and correlation with possible disease mechanisms
- Analysis of faecal fungi in relapse of IBD

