6 ELIGIBILITY CRITERIA

6.1 Inclusion criteria

- Children (age <18 years) capable of giving informed consent, or if age < 16 years or not capable of giving consent, with an acceptable individual capable of giving consent on the child's behalf
- 2. Children of either gender attending a paediatric gastroenterology referral clinic in whom IBD is suspected following initial clinical assessment [1]
- 3. Further evaluation planned to diagnose the cause of the child's illness
- 4. Willing for demographic and clinical information to be used for the purposes of the study
- 5. Willing for part of the stool sample provided for routine clinical assessment to be used for the measurement of VOCs []]

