6.2 Exclusion criteria

- 1. Treatment already received for IBD (e.g. polymeric formula feeds in children awaiting investigation)
- 2. Established diagnosis of a significant gut disorder (e.g. short bowel syndrome)
- 3. Failure to obtain informed consent from the young person or parent/guardian

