7.7 Trial assessments

A diagnosis of IBD will be based on gastrointestinal endoscopy and biopsy and imaging and IBD type classified according to standard clinical guidelines (Crohn's disease, ulcerative colitis, indeterminate colitis; Levine 2014). The distribution of disease and associated manifestations (e.g. presence of fistulas) in CD will be classified according the Paris classification (Levine 2011). The severity of IBD at initial diagnosis will be graded according to paediatric-specific disease activity scores: weighted Paediatric Crohn's Disease Activity Index (wPCDAI) and Paediatric Ulcerative Colitis Activity Index (PUCAI; Ruemmele 2014). Treatment of IBD will be provided by clinical staff and follow established clinical guidelines.

For other conditions, specific investigations and diagnosis will be guided by clinical assessment; e.g.

Faecal volatiles in children with inflammatory bowel disease

serum anti-tissue transglutaminase antibodies and/or small bowel biopsy for the diagnosis of coeliac disease; stool bacterial culture for infectious diarrhoea. Appropriate treatment will be provided by clinical staff.

The clinical records of all children will be reviewed at 3 months after recruitment and information regarding results of investigations and diagnosis/diagnoses will be recorded.

In children with IBD, a further stool sample will be requested at 3 months. This will be used for measurement of faecal calprotectin as part of routine clinical care and, if young people or parents/guardians agree, for repeat measurement of VOCs as described above. Treatment received will be recorded and current disease activity determined. Clinical remission in CD will be defined as a wPCDAI ≤12.5 and in UC as PUCAI <10 points in the absence of corticosteroid treatment (Ruemmele 2014).

- 7.8 Long term follow-up assessments: Participants will not be followed-up after 3 months.
- 7.9 Qualitative assessments Nested studies: N/a
- 7.10 Withdrawal criteria: N/a

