16.4 Appendix 4 – Schedule of Procedures

Procedures	Visits		
	Screening/Baseline	Follow Up	
	Visit 1	Visit 2; 3 months	
Informed consent	x		
Demographics	x		
Medical history	x		
Physical examination	x		
Eligibility assessment	x		
Arrangements for clinical investigations as required for routine clinical management (e.g. faecal calprotectin, endoscopy)	x		
Faecal sample collected for VOCs analysis	x		
Concomitant medications	x		
Confirmation of diagnosis		х	
In confirmed IBD: disease classification, distribution, severity at baseline (from medical records)		х	
In confirmed IBD: previous and current treatment; concomitant medications		х	
In confirmed IBD: assessment of clinical remission (disease activity scores)		х	
In confirmed IBD: faecal sample collected for VOCs analysis		х	

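### The relapse part of the mycobiome hypothesis, question, objective and endpoint cannot be answered by a design with one assessment after presentation

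*Protocol*

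**What the plan says.** Relapse appears at every level of the mycobiome work in the protocol:

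- Section 2, hypothesis 3: "the faecal mycobiome will be altered during relapse".
- Section 3, third main research question: "How does the faecal mycobiome change during relapse and what is the relationship to the VOCs".
- Section 3.2, fourth secondary objective: "To explore the relationship between fungi, relapse and VOCs".
- Section 3.3, secondary endpoint: "Analysis of faecal fungi in relapse of IBD". Section 3.5, item 3, takes this up and says a positive finding would open the way to probiotic or antifungal treatment.

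The design is as follows:

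- Section 6.1 admits children "in whom IBD is suspected following initial clinical assessment". Section 6.2 excludes those with "Treatment already received for IBD" and those with an established significant gut disorder.
- Sections 7.7 and 7.11 and Appendix 4 provide a stool sample at presentation and, in confirmed IBD only, one more at 3 months. Section 1 ties the mycobiome to the same samplings as the VOCs.
- Disease activity is graded at initial diagnosis and again at the 3-month visit (3.5, 7.7, Appendix 4).
- Section 7.8: "Participants will not be followed-up after 3 months".
- At 3 months the protocol defines clinical remission by wPCDAI or PUCAI (3.5, 7.7). It calls the alternative persistent disease (sections 2, 3 and 3.2). It gives no definition of relapse.

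**The concern.** Relapse means that disease became active again after a remission. A cohort recruited at first presentation and looked at once afterwards has no documented remission from which to relapse. If a result is nevertheless reported under this endpoint, the only groups available to stand in for relapse are active disease at presentation and non-remission at 3 months. Neither is relapse: one is new, untreated disease and the other may be disease that never remitted. Calling either of them relapse would give a wrong conclusion about fungi in IBD, on an item to which section 3.5 attaches possible treatment implications.

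A separate statistical analysis plan cannot repair this, because eligibility, sampling times and length of follow-up are fixed in the protocol. Section 10.3.3 applies analyses similar to the primary one, a comparison of groups, but no relapse group can be formed. Section 10.7 defines an analysis set for response to treatment and none for relapse.

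**Working it through.** The protocol gives no power or sample size figure for this item. The check sets what a relapse requires against what the schedule observes.

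**Inputs**
- Planned recruitment: 286 children, with IBD confirmed in 1 in 2 (section 10.1).
- Planned IBD cases: 286 × 0.5 = 143, which agrees with section 10.2.
- Scheduled stool and activity time points per IBD case: 2, at presentation and at 3 months (7.7, Appendix 4).
- Ordered states needed to document a relapse: 3 (active, remission, active).

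**Step 1: could a child enter in relapse?** Treated IBD is excluded by 6.2, and so is an established significant gut disorder. Entry requires only suspected IBD. Presentation is therefore the first documented active state, with no recorded remission before it.

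**Step 2: could a relapse be documented after entry?** One observation follows presentation. The possible sequences and what the schedule records are:

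| True course up to 3 months | Recorded at presentation | Recorded at 3 months |
|---|---|---|
| Active, then remission | active | remission |
| Active throughout | active | not in remission |
| Active, remission, active again | active | not in remission |

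The second and third rows have the same record. A child who relapsed cannot be told from one who never remitted.

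**Step 3: count.** Two time points are fewer than the three states needed, so the scheduled assessments document 0 relapses out of 143 planned IBD cases. More recruitment would not change this, because the limit lies in the number of assessments per child.

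**Step 4: what remains answerable.** With stool and an activity score at both times, the samples support three analyses in children with IBD: the correlation of fungi with VOCs, the within-child change from presentation to 3 months, and the comparison of remission with persistent disease at 3 months.

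**The case against.** The strongest reply is that the mycobiome work is exploratory and loosely worded. Section 2 speaks of a temporal relation between fungi, VOCs and disease activity, and hopes only to speculate about relapse. Section 3.2 says explore, and 3.5 says a change may be associated with relapse. Section 1 commits simply to studying VOCs and fungi in these children. On this reading relapse is shorthand for active disease. The item is also missing from the trial summary and does not touch the primary objective or the sample size.

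Much of this stands. It limits both the scope and the weight of the point. A reader might infer that the whole mycobiome objective fails. The documents do not support that: the second half of research question 3, on the relation to VOCs, and the link with disease activity can be addressed with the planned samples. A reader might also infer that the trial intends to relabel persistent disease as relapse. The protocol plans no such thing and keeps the two terms apart. The risk comes from an endpoint left without a group to fill it.

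A further reply is that the 3-month record review (7.7) and the record of previous and current treatment (Appendix 4) might reveal an intervening flare. They might in individual cases. Without a definition of relapse, a scored remission before it or a stool sample taken at that time, such a note would not supply the endpoint.

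The shorthand reading does not rescue the wording. Relapse is named in a hypothesis, in one of three main research questions, in an objective and in an endpoint. The caution in section 2 is a reason to bring those four into line with it.

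**Conclusion.** The point holds for the relapse component only. Under the schedule as written, 0 of the planned 143 IBD cases would have a documented relapse, and any early relapse would be merged with persistent disease. This rests on the ordinary meaning of relapse as renewed disease after remission, and on Appendix 4 being the full set of study assessments. It does not mean that no child will relapse within 3 months. The documents give no rate for that, and the conclusion does not need one.

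The fungi–VOC relation and its link to disease activity remain within reach, and the primary objective, sample size and VOC analyses are unaffected. The wording should be corrected, but the point does not threaten the main purpose of the study.

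**What to change.** In sections 2, 3, 3.2, 3.3 and 3.5 (item 3), replace relapse with what the two samples can show in children with IBD: the within-child change in the mycobiome from presentation to the 3-month sample, by clinical remission versus persistent disease, and its correlation with VOCs. State that no conclusion on relapse will be drawn. Report the number of children with both samples, since the second is requested and its research use depends on agreement (7.7), so the paired set may be smaller than 143.

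Add a comparison of the mycobiome at presentation between IBD and non-IBD children only if the non-IBD stools are already to be sequenced. The protocol does not make this clear, and otherwise it would add laboratory cost.

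Cost: a wording amendment, with no new visits, samples or participants. Studying relapse itself would need a definition, follow-up able to observe it and a sample tied to it, which is a larger change than this point requires.
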